13.16 Medication error

For the purposes of this clinical study a medication error is an unintended failure or mistake in the treatment process for an AstraZeneca study drug that either causes harm to the patient or has the potential to cause harm to the patient.

A medication error is not lack of efficacy of the drug, but rather a human or process related failure while the drug is in control of the study site staff or patient.

TRIPLEX
1.1

Medication error includes situations where an error

- Occurred
- Was identified and intercepted before the patient received the drug
- Did not occur, but circumstances were recognized that could have led to an error

Examples of events to be reported in clinical studies as medication errors:

- Drug name confusion
- Dispensing error e.g. medication prepared incorrectly, even if it was not actually given to the patient
- Drug not administered as indicated, for example, wrong route or wrong site of administration
- Drug not taken as indicated e.g. tablet dissolved in water when it should be taken as a solid tablet
- Drug not stored as instructed e.g. kept in the fridge when it should be at room temperature
- Wrong patient received the medication
- Wrong drug administered to patient

Examples of events that do not require reporting as medication errors in clinical studies:

- Errors related to or resulting from IVRS/IWRS including those that lead to one of the above listed events that would otherwise have been a medication error
- Patient accidentally missed drug dose(s) e.g. forgot to take medication
- Accidental overdose (will be captured as an overdose)
- Errors related to background and rescue medication, or standard of care medication in open label studies, even if an AZ product

Medication errors are not regarded as AEs, but AEs may occur as a consequence of the medication error. If a medication error occurs during the study, the Investigator or other site personnel must inform Sponsor within 1 day i.e., immediately but no later than 24 hours of when he or she becomes aware of it. The Sponsor works with the Investigator to ensure that all relevant information is completed within 1 or 5 calendar days. The Sponsor must report to AstraZeneca Patient Safety using the designated Safety emailbox within 7 calendar days or sooner when required if there is an SAE associated with the medication error and within 30 days for all other medication errors.

14. Endpoints, statistical methods and sample size determination

14.1 Endpoints

Primary endpoint

• 1-year overall survival

Secondary endpoints

- 2-year, 3-year, 4-year and 5-year overall survival.
- Overall response rates
- Response rates in non-irradiated lesions
- Progression free survival
- Progression free survival in non-irradiated lesions
- Local control rates in the thorax
- Frequency and severity of adverse events
- Health-related quality of life

Exploratory endpoints

- Duration of severe adverse events
- Frequency and timing of brain metastases
- Assess cognitive function in the whole study cohort and compare cognitive function between patients who receive PCI and those who do not.
- Associations between outcomes of study treatment and biomarkers in tissue, blood and stool (e.g. ctDNA in blood, miRNA and gut microbiome).

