1. PROTOCOL SYNOPSIS

Study title: Randomized phase III trial investigating the survival benefit of adding thoracic radiotherapy (TRT) to durvalumab immunotherapy plus chemotherapy in extensive stage small-cell lung cancer

Protocol version number: 1.0

Clinical phase: Randomized phase III

Study duration: From 2021 until 2028

Investigational therapies and reference therapy:

- Reference therapy: Durvalumab plus carboplatin/etoposide
- Investigational therapy: Durvalumab plus carboplatin/etoposide and TRT

Research hypotheses:

The main hypothesis is that adding TRT to durvalumab plus chemotherapy provides a survival benefit for patients with extensive stage (ES) small-cell lung cancer (SCLC).

Specifically, we hypothesize that:

- combining TRT, durvalumab and chemotherapy is feasible and well tolerated
- adding TRT improves survival, response rates, and PFS
- the patients who benefit the most from the study treatment can be identified through analyses of tissue, blood and stool samples
- toxicity of prophylactic cranial irradiation (PCI) is acceptable in ES SCLC patients who receive durvalumab plus chemotherapy

Objectives:

Primary Objective:

To investigate whether adding TRT to durvalumab plus chemotherapy improves 1-year survival.

Secondary Objectives:

To investigate whether adding TRT improves 2-, 3-, 4- and 5-year overall survival.

To investigate whether adding TRT improves overall response rates, response rates in non-irradiated lesions and PFS.

To investigate whether TRT improves local control.

To compare the frequency and severity of adverse events between the treatment arms.

To compare health related quality of life between treatment arms.

Exploratory Objectives:

To compare the duration of severe adverse events between the treatment arms.

To compare the frequency and timing of brain metastases between treatment arms.

To assess cognitive function in the whole study cohort and compare cognitive function between those who receive PCI and those who do not.

To investigate associations between outcomes of study treatment and biomarkers in tissue, blood and stool (e.g. ctDNA in blood, miRNA, gut microbiome).

Endpoints:

Primary Endpoint:

1-year overall survival

Secondary Endpoints:

2-year, 3-year, 4-year and 5-year overall survival

Overall response rates

Response rates in non-irradiated lesions

Progression free survival

Progression free survival in non-irradiated lesions

Local control rates in the thorax

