4.1.2 Treatment of SCLC

Patients with localized disease (T1-2N0) are offered surgery followed by adjuvant chemotherapy and/or radiotherapy and prophylactic cranial irradiation, but very few (approx. 5 per year in Norway) are operable since most have regional or metastatic disease at the time of diagnosis. For inoperable patients, chemotherapy is the main treatment, and platinum/etoposide remains the standard regimen, at least in the western world. A Japanese trial showed that platinum/irinotecan was superior to platinum/etoposide in ES SCLC, but the relatively large survival benefit was not confirmed in trials performed in other countries. A possible explanation is differences in pharmacogenomics. A meta-analysis showed a small benefit of platinum/irinotecan over platinum/etoposide in terms of survival but was mainly driven by Asian studies. Thus, platinum/etoposide remains the standard regimen in the Western world.

Concurrent chemotherapy and TRT is superior to chemotherapy alone when all lesions can be included in a RT field (limited stage, "LS SCLC").¹⁵ Chemotherapy alone has until recently been the standard treatment for patients with more widespread disease (extended stage, "ES SCLC").⁹ Prophylactic cranial irradiation (PCI) reduces the frequency of brain metastases and prolongs survival in LS patients who respond to the primary treatment.¹⁶ The role of PCI is more debated in patients with ES. One European study showed that PCI reduces the risk of brain metastases and prolongs survival in this setting,¹⁷ while a Japanese study did not confirm the survival benefit, suggesting that active surveillance is a better approach than PCI.¹⁸

Up to 90% of LS patients respond and 25-30% are cured by chemoradiotherapy and are alive after 5 years. ^{19,20} The response rate is lower for ES SCLC (approx. 65%), almost all patients relapse within 1-2 years, and the 5-year survival is around 3%. ⁵ There have been major improvements in treatment outcomes for NSCLC, but the survival rates for SCLC have remained more or less unchanged the last 20 years. ^{2,21}

One reason for the lack of progress is that most lung cancer research focuses on NSCLC. At the ASCO annual meeting 2020, 6300 abstracts were submitted. Of these, 512 reported lung cancer research, but only 22 (4.3%) concerned SCLC. The poor survival, the low 5-year survival, the lack of progress, research and new therapies for SCLC underscores the need for research on this orphaned disease.

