4.3 Research hypotheses

The main hypothesis is that adding TRT to chemotherapy plus durvalumab provides a survival benefit for patients with extensive stage (ES) small-cell lung cancer (SCLC). Specifically, we hypothesize that:

- combining TRT, chemotherapy and durvalumab is feasible and well tolerated
- adding TRT improves 1- and 2-year survival, median OS, response rates, and PFS
- the patients who benefit the most from the study treatment can be identified through analyses of tissue, blood and stool samples
- PCI is well tolerated, reduces the risk of brain metastases and prolongs survival in ES SCLC patients who
 receive chemotherapy plus durvalumab compared with patients who do not receive PCI

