4.4 Rationale for conducting this study

- Chemotherapy plus an PD-L1 inhibitor is considered a new standard of care for first-line treatment of ES SCLC but is not yet available/reimbursed in all countries. Durvalumab plus platinum/etoposide is one of these new standard regimens. However, the survival benefit is limited, especially for the first 6 months, and a more effective treatment is needed.
- A more effective initial therapy might improve survival the first 6 months and long-term survival.
- It has been demonstrated that TRT improves survival in ES SCLC, and the effect in terms of PFS is immediate.
- Several studies suggest a synergistic effect of combining RT and ICI. Concurrent administration appears to be the most effective approach, and we will administer the TRT between the second and third chemoimmunotherapy courses. This is deemed to be the earliest time point that TRT may be administered at all sites. We know that SCLC patients may achieve a substantial response to one chemotherapy course (*Halvorsen*, 2016) and believe that administering TRT earlier than in the CREST trial will make it easier to locate the target lesions, increases the likelihood of irradiating viable tumor cells, and consequently increase the chance for achieving a synergistic effect of the TRT and the immunotherapy and not merely an additive effect.
- Combining high-dose TRT, platinum doublet chemotherapy and ICI appears to be well tolerated. Thus, combining medium dose TRT with durvalumab and carboplatin/etoposide should be feasible and well tolerated. However, since there is no data on this combination, investigating whether ading TRT increases the frequency or severity of side effects is an essential part of this trial.
- The benefits and tolerability of PCI in ES SCLC patients receiving chemotherapy plus ICI are unknown.
 We will compare the timing and frequency of brain metastases between patients who receive PCI and those who do not. Furthermore, we will measure and compare cognitive function before and after PCI.
- The survival benefit from adding ICI does not appear before after 6 months. Thus, we restrict the protocol for patients in performance status 0-1. In a previous trial on chemotherapy in ES SCLC, median OS was below 6 months among patients with a PS of 2 or more.

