8.4 Prophylactic cranial irradiation (PCI)

PCI is not mandatory, but patients who respond to chemoimmunotherapy and have not previously received brain irradiation, should be offered PCI at the hospitals where this is established treatment of ES SCLC.

PCI should start between 4 to 6 weeks after the last chemoimmunotherapy course. PCI should be administered according to local routines. Hippocampus-sparing PCI is allowed. Recommended schedules are 25 Gy in 10 fractions or 30 Gy in 15 fractions. One schedule should be used for all patients at each site. PCI may be administered concurrently with durvalumab infusions.

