8.4.1 Treatment of brain metastases

The treatment of brain metastases varies between hospitals. Patients with brain metastases may receive whole brain radiotherapy (WBRT) before or after chemoimmunotherapy. Recommended schedules are 30 Gy in 10 fractions (preferred) or 20 Gy in 4-5 fractions. WBRT should be administered according to local routines. WBRT may be offered patients who have received PCI if this is the local treatment policy.

An alternative to WBRT is stereotactic radiosurgery (SRS) provided the number, size and location of the brain metastases allows for SRS. The role of SRS in brain metastases from SCLC is less defined than for NSCLC, but especially for patients who have received PCI, have good and long extracranial disease control, and limited number of brain metastases, SRS may be a better alternative than WBRT. Surgery may be an alternative but is seldom offered SCLC patients.

Isolated progression in the brain does not necessarily warrant a change in systemic treatment provided local control is achieved by SRS, WBRT or surgery.

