14.3.3 Exploratory analyses

Cognitive function (MoCA-scores) will be compared using the Mann-Whitney test, and time until decline of MoCA-scores will be compared. Associations between biomarkers in tissue, blood and stool samples, and treatment outcomes, baseline characteristics, and survival will be investigated. A detailed project plan including biomarker and data analysis plan will be defined when sufficient biological material and clinical data to start the translational research have been collected.

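### The exploratory cognition comparison sets PCI recipients, who are responders by rule, against everyone else, including non-responders and patients given whole-brain radiotherapy

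*Protocol*

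**What the plan says.** The exploratory objective in the synopsis is to "compare cognitive function between those who receive PCI and those who do not", and the endpoint list in section 14.1 repeats it: "Assess cognitive function in the whole study cohort and compare cognitive function between patients who receive PCI and those who do not". Neither place limits who may enter the group without PCI.

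On method, section 14.3.3 states: "Cognitive function (MoCA-scores) will be compared using the Mann-Whitney test, and time until decline of MoCA-scores will be compared". It does not name the groups for that test.

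Who gets PCI is set in section 8.4: "patients who respond to chemoimmunotherapy and have not previously received brain irradiation, should be offered PCI", and only at hospitals where PCI is established for this disease. The synopsis also ties the offer to response after chemo-immunotherapy.

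Patients with asymptomatic or treated and stable brain metastases are eligible (inclusion criterion 13, section 7.1). Section 8.4.1 adds: "Patients with brain metastases may receive whole brain radiotherapy (WBRT) before or after chemoimmunotherapy".

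Sections 4.4 and 5.2 plan a separate measurement of cognition before and after PCI. Section 4.4 also says: "We will compare the timing and frequency of brain metastases between patients who receive PCI and those who do not". That comparison is not in the list of endpoints.

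**The concern.** A contrast between treated and untreated patients is informative only if the untreated could have been treated. Here the offer rule makes PCI recipients responders with no earlier brain irradiation, and the comparator carries no matching limit. The two groups therefore differ by design on three things that can each affect a MoCA score: tumour response, disease in the brain, and irradiation of the whole brain.

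At stake is one of the trial's stated side questions. Section 4.2.9 says that the cognitive effect of PCI given with checkpoint inhibition is unknown, and that the only data come from a 44-patient subgroup without assessment of long-term neurocognitive decline. A comparison built as written could suggest that PCI is harmless, or harmful, for reasons unrelated to PCI.

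**Working it through.** No stated figure can be reproduced, so the first step is to set the rules side by side.

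| Feature | PCI recipients | Everyone else | Source |
|---|---|---|---|
| Response after chemo-immunotherapy | Responders, by the offer rule | Responders not given PCI, plus all non-responders | Synopsis, 8.4 |
| Brain metastases | Not intended, since PCI is prophylactic | May be present from baseline | 7.1, 8.4, 8.4.1 |
| Brain irradiation before the PCI decision | Ruled out by the offer rule | Possible | 8.4, 8.4.1 |
| WBRT later on | Possible; may be offered after PCI | Possible | 8.4.1 |
| Recommended whole-brain dose | PCI: 25 Gy in 10 or 30 Gy in 15 fractions | WBRT, if given: 30 Gy in 10 or 20 Gy in 4-5 fractions | 8.4, 8.4.1 |

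Exclusion criterion 3 bars previous radiotherapy for SCLC. Read literally, it narrows the group irradiated before entry, but it does not affect WBRT given on study.

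**Does another section correct for this?** The covariates in section 14.3.2, which include brain metastases, belong to the Cox models for the efficacy outcomes. A Mann-Whitney test uses no covariates. The schedule in section 2 gives MoCA to the whole cohort at screening, weeks 11-12 and week 21, at later visits, and at progression. Non-responders and WBRT recipients therefore contribute scores.

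**Illustration of the mix at week 11-12.** Inputs:

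- N = 302 (section 14.4).
- Response rate r = 0.65 (section 4.1.2, stated for ES SCLC treatment before immunotherapy).
- PCI uptake u among responders: assumed, because the protocol gives none.

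Non-responders: 302 × 0.35 = 105.7. Responders: 302 × 0.65 = 196.3.

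Share of non-responders without PCI = 105.7 / (105.7 + 196.3 × (1 − u)).

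- u = 0.25: 105.7 / 252.9 = 41.8%
- u = 0.50: 105.7 / 203.8 = 51.9%
- u = 0.75: 105.7 / 154.8 = 68.3%

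With an assumed r = 0.75, non-responders number 75.5 and the shares are 75.5 / 245.4 = 30.8%, 75.5 / 188.8 = 40.0% and 75.5 / 132.1 = 57.1%. Under the offer rule the share among PCI recipients is 0%.

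**What the illustration does not show.** PCI starts in weeks 13-15, so the week 11-12 MoCA precedes it. The first scheduled MoCA afterwards is at week 21. Patients who stop study treatment for progression are then followed by local practice (section 2), so many progressing non-responders will have left the MoCA schedule by then. The share will be lower at every visit where a PCI effect could appear, and the protocol has no figure from which to say how much lower.

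**Direction.** Non-response and brain metastases in the comparator may lower its scores and make PCI look harmless. Whole-brain irradiation in the comparator, at total doses overlapping those of PCI, may also lower its scores and hide a real PCI effect. Patients selected for WBRT or spared PCI may differ in other ways too, so the net direction cannot be predicted.

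**The case against.** The strongest reply is that this is detail for the statistical analysis plan. Section 14.1 is a list of endpoints, not a definition of analysis sets, and a plan that is not shown may restrict the comparator or set a landmark. This stands in part: the text does not prove that the final analysis will be unrestricted. But the protocol is not silent. It states the contrast without a limit and names an unadjusted test. The further plan promised in section 14.3.3 is described for the biomarker and translational work.

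A reader might infer that section 14.3.3 fixes the groups together with the test. It does not: the groups come from the synopsis and section 14.1, and time until decline has no stated method.

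A reader might also take the shares above as bounds on the bias. They are not. They rest on assumed uptake and describe a visit before PCI.

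The within-patient comparison before and after PCI avoids the comparator problem, so the PCI question does not rest on this contrast alone. That stands. So does the point that later WBRT can occur in both groups.

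Finally, PCI depends on hospital policy and patient choice, so even a restricted comparison is not causal. That is true, but restriction removes known differences that can be avoided.

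**Conclusion.** The point holds as a minor, cheap improvement. Followed as written, the PCI versus no-PCI comparison of MoCA scores is confounded by response, brain disease and whole-brain irradiation, and neither a difference nor its absence could be attributed to PCI. The size cannot be computed from the protocol. The conclusion rests on the wording of the offer rule, the eligibility of patients with brain metastases and the permission for WBRT, not on the illustrative shares.

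Two stronger readings are not supported. A reader might infer that PCI versus no-PCI comparisons of brain metastases and survival are planned endpoints. They appear only in the hypothesis in section 4.3 (patients who "receive chemotherapy plus durvalumab compared with patients who do not receive PCI") and, for brain metastases, in the rationale in section 4.4; the listed objective compares brain metastases between treatment arms. A reader might also infer from section 8.4, which does not mention absence of brain metastases, that patients who have them could be given PCI. The word prophylactic, section 8.4.1 and the brain scan at weeks 11-12 make the intent plain.

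The before-and-after PCI comparison, the primary endpoint, alpha, power and all randomised comparisons are unaffected.

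**What to change.** Add one sentence to section 14.3.3, or to the analysis plan. Limit the PCI versus no-PCI comparison of MoCA scores to patients who are responders at the week 11-12 evaluation, have no brain metastases at baseline or on that scan, and have had no WBRT or stereotactic radiosurgery before that point. Compare at visits from week 21 onward, and report patients given WBRT or radiosurgery separately. If the brain-metastasis comparison mentioned in section 4.4 is carried out, apply the same restriction, because patients who already have brain metastases cannot inform the risk of developing them.

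The change needs no new data. The brain-metastasis stratification factor, the week 11-12 response evaluation and brain scan, and the radiotherapy records are already planned. The cost is a smaller exploratory comparison that is still non-randomised and should be reported as such.

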4.2.9 Prophylactic cranial irradiation in ES SCLC

Whether PCI is beneficial for patients who receive combined immunotherapy and chemotherapy is unknown. It is unknown whether receiving checkpoint inhibitor therapy increases the potential detrimental cognitive effect of PCI, and the benefit of PCI may be reduced due to improved disease control due to the improved efficacy of the triple combination.

The only available data on PCI in patients receiving ICI, are from a subgroup analysis of the 44 patients who received PCI as part of the Impower 133 trial. There were no indications of more side effects among those who received PD-L1 inhibitor therapy, but the cohort was small and follow-up did not include assessment of long-term neurocognitive decline.⁵⁸

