- 10. Stage IV disease according to the TNM v8. Patients with stage III disease are eligible if the disease is too widespread to be treated as LS SCLC.
- 11. Pulmonary function: FEV1 >1 L or >30 % of predicted value and DLCO >30 % of predicted value.
- 12. Female patients of childbearing potential (postmenarcheal, not postmenopausal [>12 continuous months of amenorrhea with no identified cause other than menopause], and no surgical sterilization) should use highly effective contraception and take active measures to avoid pregnancy while undergoing systemic study therapy and for at least 5 months after the last dose.
- 13. Patients with brain metastases are eligible provided they are asymptomatic or treated and stable on steroids and/or anticonvulsants prior to start of treatment.

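### The no-PCI group in the exploratory MoCA comparison mixes patients without brain irradiation and patients given whole-brain radiotherapy, so the contrast does not isolate PCI and probably, but not certainly, dilutes its effect

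*Protocol*

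**What the plan says.** - **Comparison.** The synopsis and Protocol 14.1 (exploratory endpoints) plan to "compare cognitive function between patients who receive PCI and those who do not".
- **Method.** Section 14.3.3: "Cognitive function (MoCA-scores) will be compared using the Mann-Whitney test, and time until decline of MoCA-scores will be compared". No restriction of either group is stated.
- **Who is offered PCI.** Section 8.4: "patients who respond to chemoimmunotherapy and have not previously received brain irradiation, should be offered PCI at the hospitals where this is established" practice.
- **Who may have WBRT.** Brain metastases are a stratification factor (9.1.1), and section 7.1 admits these patients: "Patients with brain metastases are eligible provided they are asymptomatic or treated and stable on steroids and/or anticonvulsants prior to start of treatment". Section 8.4.1 adds: "Patients with brain metastases may receive whole brain radiotherapy (WBRT) before or after chemoimmunotherapy". It also permits WBRT after PCI where that is local policy, and names radiosurgery and surgery as alternatives.
- **Timing.** The schedule in section 2 has MoCA at screening and week 11-12, start of PCI at weeks 13-15, and MoCA again from week 21. Brain imaging is due at screening and week 11-12.
- **Premise.** Section 4.2.9 calls it unknown whether checkpoint inhibition "increases the potential detrimental cognitive effect of PCI".

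**The concern.** The question is whether PCI harms cognition in patients on chemo-immunotherapy. That calls for a reference group comparable with the PCI group but without cranial irradiation. The planned reference group is everyone else, and the protocol's own rules place in it patients whose whole brain was irradiated to treat metastases. The total doses are of a similar order: for WBRT, "Recommended schedules are 30 Gy in 10 fractions (preferred) or 20 Gy in 4-5 fractions"; for PCI, section 8.4 recommends 25 Gy in 10 or 30 Gy in 15 fractions.

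If WBRT or the metastases lower MoCA, the reference mean falls and the gap to the PCI group narrows. The trial hypothesises that PCI toxicity is acceptable (synopsis) and that PCI is well tolerated (4.3). A narrowed gap would favour those hypotheses, which is the less safe direction of error for a question about harm.

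**Working it through.** The protocol states no sample size, effect size, standard deviation or WBRT rate for the MoCA comparison, so there is no planned figure to reproduce. The check has two parts.

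**1. Who ends up in which group, from the text**

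| Patient | Group |
|---|---|
| WBRT before the PCI time point | no PCI only (8.4 excludes earlier brain irradiation from the PCI offer) |
| Brain metastases, no brain irradiation, responder | either; 8.4 does not exclude on metastases alone |
| Non-responder | no PCI |
| Responder at a hospital that does not use PCI | no PCI |
| WBRT after the PCI time point | either group (8.4.1 allows WBRT after PCI) |

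The first row is the asymmetry. A patient given early WBRT for metastases present at entry has not progressed on that account and stays on the MoCA schedule, so the scores will be collected. WBRT given after the week 11-12 MoCA is not removed by adjusting for that score.

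**2. Direction and possible size (illustrative)**

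All inputs here are assumptions:
- *d*: true PCI effect on MoCA, in SD
- *r*: WBRT effect divided by PCI effect
- *w*: share of the no-PCI group given WBRT
- *v*: share of the PCI group later given WBRT, with its effect added to that of PCI

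Relative to unirradiated patients, the no-PCI mean is lowered by *w·r·d* and the PCI mean by *d + v·r·d*. The observed difference is *d + v·r·d − w·r·d*, so

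observed / true = 1 − *w·r* + *v·r*.

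With no WBRT after PCI (*v* = 0):

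| *w* | *r* = 0.5 | *r* = 1 | *r* = 1.5 |
|---|---|---|---|
| 5% | 0.975 | 0.95 | 0.925 |
| 10% | 0.95 | 0.90 | 0.85 |
| 20% | 0.90 | 0.80 | 0.70 |
| 30% | 0.85 | 0.70 | 0.55 |
| 40% | 0.80 | 0.60 | 0.40 |

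With WBRT in both groups (*r* = 1):

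| *w* | *v* | observed / true |
|---|---|---|
| 20% | 5% | 1 − 0.20 + 0.05 = 0.85 |
| 20% | 10% | 1 − 0.20 + 0.10 = 0.90 |
| 20% | 20% | 1 − 0.20 + 0.20 = 1.00 |
| 10% | 20% | 1 − 0.10 + 0.20 = 1.10 |

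On the scale of the planned test, the Mann-Whitney probability under normal scores is Φ(*d*/√2) without WBRT. With WBRT in the no-PCI group only, it is (1 − *w*)·Φ(*d*/√2) + *w*·Φ((*d* − *r·d*)/√2). For *d* = 0.5, *r* = 1 and *w* = 20% it falls from 0.638 to 0.8 × 0.638 + 0.2 × 0.5, about 0.611. For *d* = 0.3 it falls from 0.584 to 0.567.

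Dilution is thus the result when WBRT is commoner in the no-PCI group. It vanishes when the shares are equal and reverses when WBRT is commoner after PCI.

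**The case against.** A reader might infer four stronger claims that the protocol does not support.

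- **That the harm of PCI is certainly understated.** WBRT after PCI works the other way, and the protocol gives neither shares nor effects. Section 4.2.9 also calls the harm only potential, so it cannot be treated as established.
- **That every patient with brain metastases falls in the no-PCI group.** Section 8.4 turns on earlier brain irradiation, not on metastases. WBRT is optional and other local treatments are named.
- **That WBRT after later progression adds heavily to the problem.** MoCA is done at progression, but patients who stop study treatment for progression then follow local routine (notes to the schedule). Their MoCA after WBRT is mostly unscheduled. The exception is isolated brain progression with study treatment continued (8.4.1).
- **That all scores after later metastases or WBRT should be removed.** Section 4.3 hypothesises that PCI reduces brain metastases, so removal would condition on something PCI is meant to change and would discard any cognitive benefit of avoiding them.

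Other objections carry some weight. Sections 4.4 and 5.2 also plan a comparison before and after PCI, which does not use this comparator; but it has no control for time, disease or systemic treatment and is not set out in 14.3.3. Exclusion criterion 3 in 7.2 (previous radiotherapy for SCLC), read strictly, would narrow the route through WBRT before randomisation. It sits uneasily with inclusion criterion 13 and section 8.4.1, and those passages must be reconciled. WBRT after randomisation but before the PCI time point remains possible either way. Finally, details of an exploratory analysis often belong in an analysis plan. Here, however, the protocol itself fixes the two groups, and applying them as written gives the mixed comparator.

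**Conclusion.** The point holds as one of confounding. The comparator is defined only by absence of PCI, and WBRT before the PCI time point can fall only on that side, so the comparison does not set PCI against no cranial irradiation. Dilution of a PCI effect is the likelier direction because of that asymmetry, but it is not assured.

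The size is unknown. The range of 0.975 to 0.40 of the true effect assumes that WBRT lowers MoCA by 0.5 to 1.5 times the PCI effect, that 5-40% of the no-PCI group receives it, and that nobody has WBRT after PCI. The last assumption is the one most open to challenge, since relaxing it can bring the ratio to 1.00 or above. The endpoint is exploratory and PCI is not randomised, so this is a minor improvement and does not touch the primary analysis.

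**What to change.** Add to section 14.3.3:

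- The main PCI versus no-PCI comparison of MoCA is limited, in both groups, to patients with no brain metastases on the screening and week 11-12 brain imaging and no brain irradiation before the PCI time point (weeks 13-15 in the schedule). Preferably it is limited further to responders at week 11-12, the group to whom PCI is offered.
- The unrestricted comparison is shown alongside.
- Any analysis that censors scores at later brain metastases or WBRT is a sensitivity analysis only, because PCI may itself change those events.

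Brain imaging, response and MoCA at these times are already scheduled. The case report form must also hold the dates of brain irradiation given during study treatment; section 8.5 already asks for all radiotherapy after study treatment. The cost is a few sentences and a smaller comparison group, by an amount the protocol does not allow one to estimate. Restriction does not remove selection by hospital policy or by patient and physician choice, so the result stays exploratory. No change to treatment is proposed.
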